The protocol, informed consent form(s), recruitment materials, and all subject materials will be submitted to the IRB for review and approval. Approval of both the protocol and the consent form must be obtained before any subject is enrolled. Any amendment to the protocol will require review and approval by the cIRB before the changes are implemented to the study. All changes to the consent form will be cIRB approved; a determination will be made regarding whether a new consent needs to be obtained from subjects who provided consent, using a previously approved consent form.

1 PROTOCOL SUMMARY

1.1 SYNOPSIS

Title: TRANScranial direct current stimulation for PPost-stroke motor Recovery- a phase II sTudy (TRANSPORT2)

Study Description: TRANSPORT2 is a phase II multi-center transcranial direct current stimulation (tDCS) dosing selection study based on the preliminary efficacy, safety, tolerability and feasibility.

Objectives: **Primary Objective:** To determine whether there is an overall treatment effect among 3 dosing groups (sham+mCIMT, 2 mA+mCIMT, and 4 mA+mCIMT) on day 15 (\pm 2 days) after the start of the intervention in the Fugl-Meyer Upper-Extremity (FM-UE) scale, a measure of motor impairment. Additional outcome measures include the Wolf-Motor-Function-Test (WMFT), a measure of functional motor activity, and the Stroke-Impact-Scale (SIS), a measure of quality of life. Sustained benefit will be assessed at day 45 (\pm 5 days) and day 105 (\pm 10 days).

Secondary Objectives: To confirm that the proposed intervention is safe (no significant differences in rate of adverse events), tolerable (no significant differences in discomfort as measured by Visual-Analog-Scale), and feasible to administer in a multi-site trial (>80% of subjects complete the treatment protocol and no unexplained/unresolved variability by site).

Exploratory Objectives: To examine whether wCST-LL (structural assessment of integrity of descending motor tract) or MEPs (functional assessment of integrity of descending motor tract) or combination of both are correlated with changes in FM-UE scale, and evaluate the utility of these measures as biomarkers for patient selection criteria in the future confirmatory Phase III study. We also

aim to examine whether structural and functional changes within descending motor tracts correlate with changes in motor impairment and functional motor activity.

Endpoints:

Primary Endpoint: Fugl-Meyer Upper-Extremity (FM-UE) scale a measure of motor impairment;

Secondary Endpoints: Wolf Motor Function Test (WMFT) time score, a measure of functional motor activity; Stroke-Impact-Scale hand subscale as an assessment of patient-centered quality of life.

Study Population:

Subject who is 18-80 years of age of any gender or ethnicity, who had first-ever unihemispheric ischemic stroke in past 30-180 days resulting in unilateral limb weakness with FM-UE ≤ 54 (out of 66) that is stable across two baseline visits at the time of randomization and an mRS ≤ 2 pre-stroke. We are planning to enroll 129 subjects across three arms.

Phase:

2

Description of Sites/Facilities Enrolling Subjects: Subject recruitment will occur at approximately 15 enrolling sites in the USA.

Subjects:

[figure not shown]
Description of Study Intervention: There are 3 intervention arms: sham, 2 mA, and 4 mA tDCS combined with modified Constrained-Induced Movement Therapy (mCIMT). The tDCS session is 30 minutes, and mCIMT is 120 minutes per session, 10 intervention sessions are completed over a 2-week (14 days) period.

Study Duration: 48 months

Subject Duration: Approximately 4 months

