3 OBJECTIVES AND ENDPOINTS

OBJECTIVES	ENDPOINTS	JUSTIFICATION FOR ENDPOINTS
------------	-----------	-----------------------------

Primary		
To determine whether there is an initial overall treatment effect among 3 dosing groups: • sham + mCIMT • 2 mA + mCIMT • 4 mA + mCIMT	FM-UE scale	FM-UE scale is the primary outcome and a measure of motor impairment
Efficacy is measured at day 15 after the initiation of the intervention.	WMFT time score	WMFT is a secondary outcome and a measure of functional motor activity
	SIS Hand Subscale	SIS Hand subscale is a secondary outcome and a measure of the quality of life
Secondary		
To confirm that the proposed intervention is safe, tolerable, and feasible to administer in a multi-site trial setting	Rate of adverse events	Safety needs to be monitored in a phase II study
	Visual Analog Scale	Visual Analog Scale measures tolerability
	Treatment completion rate	80% of treatment completion rate across sites without unexplained/unresolved variability is a measure of feasibility.
Tertiary/Exploratory		
To examine whether wCST-LL (structural assessment of integrity of descending motor tract) or MEPs (functional assessment of integrity of descending motor tract) or combination of both are correlated	wCST-LL (structural)	wCST-LL is a structural measure of integrity of descending motor tract using brain MRI that has shown promise in predicting motor outcomes.

with changes in FM-UE scale, and evaluate the utility of these measures as biomarkers for subject selection criteria in the future confirmatory Phase III study
	
MEPs (functional)
	
MEPs is a functional measure integrity of descending motor tract using TMS that has shown promise in predicting motor outcomes, but two of them have not been collected and compared in the same study.

To examine whether functional or structural changes in motor tracts correlate with changes in impairment and functional motor activity induced by the intervention.
	
Motor Evoked Potentials (MEPs) and Diffusion tensor imaging MRI.
	
MEPs can change in response to rehabilitation; Functional and structural aspects of motor tracts and the interaction between motor regions change after intervention. This change can be captured by comparing TMS and MRI measures before and after treatment

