9.4 STATISTICAL ANALYSES

Details of the statistical analyses are provided in the Statistical Analysis Plan.

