9.4.4 SAFETY ANALYSES

Safety: Analysis Method

IMSM and Data and Safety Monitoring Board (DSMB) will receive periodic safety reports of all reportable adverse events including serious adverse events (SAEs) if there are any. All clinical safety endpoints and SAEs will be summarized by AE code (as provided on the AE CRF) regarding the frequency of the event, the number of subjects having the event, severity, and relatedness to the study treatment. Clinically important adverse events include:

- Severe headache
- Second-degree skin burn
- Clinical seizure
- Neurological deterioration (\geq 4-point increase in NIHSS)

The proportion of subjects experiencing each of these events will be provided in the closed report by intervention arm with two-sided 95% CIs and unadjusted relative risks. Based on the Phase I dose-escalation study, no subjects experienced any of the clinically important adverse events. Fisher's exact tests will be used to assess intervention group differences in the rates of clinically important adverse events.

Tolerability: Analysis Method

Tolerability will primarily be measured through the use of the Visual-Analog scale (VAS), a 10-point scale ranging from 0 (No Discomfort) to 10 (Extreme Discomfort). For the primary analysis, any subject who requests to be withdrawn from the study due to procedure related issues will be imputed as a 10 on the Visual-Analog Scale. Differences in tolerability will be assessed using a Kruskal-Wallis test at a 10% type-I error rate.

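### Safety and tolerability would be confirmed by a non-significant test, yet with 43 per arm a 5-point rise in a clinically important event at one dose would be non-significant about 83–89% of the time

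*Combined protocol and SAP*

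**What the plan says.** The secondary objective in section 1.1 is to confirm that the intervention is "safe (no significant differences in rate of adverse events), tolerable (no significant differences in discomfort as measured by Visual-Analog-Scale"). The same sentence then adds a third aim, this time with a number attached: "feasible to administer in a multi-site trial (>80% of subjects complete the treatment protocol"). Section 3 repeats the aim: "To confirm that the proposed intervention is safe, tolerable, and feasible to administer in a multi-site trial setting". Feasibility therefore has a numerical threshold. Safety and tolerability are each defined by the absence of a significant result.

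Section 9.4.4 supplies the tests.

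- **Safety.** The plan lists four clinically important events: severe headache, second-degree skin burn, clinical seizure and neurological deterioration. Fisher "exact tests will be used to assess intervention group differences in the rates of clinically important adverse events". No significance level is given, and the text does not say whether the test is across three arms or pairwise.
- **Tolerability.** "Differences in tolerability will be assessed using a Kruskal-Wallis test at a 10% type-I error rate".
- **Estimation.** The proportions with each event "will be provided in the closed report by intervention arm with two-sided 95% CIs and unadjusted relative risks". No conclusion is tied to these intervals.
- **Background.** "Based on the Phase I dose-escalation study, no subjects experienced any of the clinically important adverse events". No planning rate for this trial is given.

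Section 9.2 sizes the trial on FM-UE alone. Section 9.4 defers detail to another document: "Details of the statistical analyses are provided in the Statistical Analysis Plan". No separate SAP text was available for this review.

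**The concern.** A test of no difference that fails to reject leaves open both no effect and an effect too small for the trial to see. Using that outcome as the definition of safe turns low power into success: fewer subjects, or rarer events, make the criterion easier to pass.

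This matters because section 1.1 describes a dose-selection study that rests partly on safety and tolerability. Section 2.2 says data above 2 mA are scarce in stroke patients. Section 2.3.1 names second-degree burns and seizures as theoretical risks at a high dose such as 4 mA, and both are among the four listed events. No passage makes a non-significant p-value a rule for taking a dose forward. As written, however, the trial could report 4 mA as confirmed safe on data that still allow a clinically important event in a substantial fraction of subjects.

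**Working it through.** **Inputs from the plan.** 43 per arm and 129 in total (section 9.2); 1:1:1 allocation (section 6.1.2); all randomized subjects analyzed (section 9.3); Fisher's exact test per event (section 9.4.4).

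**The plan's own sample size.** One-way ANOVA with 31 per arm, means 4.5/9.0/9.0, SD 7 and a 10% level gives 82.8% power, against 83% stated. Then 31/(1 − 0.08)² = 36.6, rounded to 37, and 37 × 1.15 = 42.6, rounded to 43. Both figures reproduce. The plan gives no power for safety or tolerability.

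**Assumptions.** Background rates of 0–5% are assumed. The level is not stated, so 5% and 10% are both shown. The test is across three arms (Fisher–Freeman–Halton), on one event, with all 43 per arm evaluable.

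**How many events are needed.** With k events, all in one arm, p = 3 × C(43,k)/C(129,k).

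- k = 2: 3 × 903/8,256 = 0.328
- k = 3: 3 × 12,341/349,504 = 0.106
- k = 4: 3 × 123,410/11,009,376 = 0.034

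If the other two arms have no events, four are needed in the third, at either level.

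**Chance of a non-significant result.** This is the sum of the binomial probabilities of all 3×2 tables with p above the level. For 0/0/5% it reduces to P(X ≤ 3) with X ~ Bin(43, 0.05) = 0.833.

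| True rates, sham/2 mA/4 mA | Level 5% | Level 10% |
|---|---|---|
| 0/0/5% | 83% | 83% |
| 2/2/7% | 86% | 83% |
| 5/5/10% | 89% | 83% |
| 0/0/10% | 36% | 36% |
| 2/2/12% | 52% | 47% |
| 5/5/15% | 67% | 56% |

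Pairwise tests of one dose against sham are weaker. For a 5-point rise from a 0–5% background they are non-significant 95–98% of the time at 5% and 90–94% at 10%.

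**Effect of sample size.** For 0/0/10% at the 5% level, the chance of passing is 36% with 43 per arm, 62% with 31 and 87% with 20.

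**What the data would still allow.**

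- 0/0/3 events meets the criterion (p = 0.106). The 4 mA rate is 3/43 = 7.0%, exact (Clopper–Pearson) 95% CI 1.5–19.1%. The difference from sham has an exact unconditional score-based 95% CI of −1.7 to +19.7 points.
- 0/43 has an upper limit of 1 − 0.025^(1/43) = 8.2% for the rate. For 0/43 against 0/43, the difference interval reaches 8.9 points. The two limits come from different interval methods, so they need not agree.

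No error rate is given for the VAS, because the plan states neither its spread nor an important shift.

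**The case against.** The strongest case against is about scope and consequence.

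- **Mismatch of criterion and test.** Section 1.1 speaks of adverse events in general, while the calculation concerns one of the four listed events. If a dose raised several of them, the chance that every test stayed non-significant would be lower than the figures above. That stands as a limit on the size, but not on the logic.
- **Choice of scenario.** No passage calls a 5-point rise important. The 89% needs a 5% level and a 5% background, whereas the level the plan does state, for the primary and tolerability tests, is 10%. At 10% the figure is about 83% throughout. A 10-point rise from zero would be detected about 64% of the time (100 − 36). These are fair qualifications.
- **Other safeguards.** The plan includes intervals and relative risks by arm, medical-monitor review of every SAE, and DSMB oversight. These protect subjects during the trial. But section 9.4.4 places the intervals in the closed report, which section 8.2.4 limits to the DSMB, the NIH liaison and the unblinded statistician. They might also appear in the final report, but nothing says so.
- **Phase II safety is descriptive, and the SAP may say more.** If it is descriptive, the objective should not say *confirm*. A margin in a SAP would still be at odds with the criterion in section 1.1 until that is reworded.

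None of these changes the stated criterion.

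**Conclusion.** The concern holds: the criterion is wrong as written, rather than merely short of detail. Under it, a non-significant result in a comparison with little power counts as confirmed safety. For one clinically important event with 43 evaluable per arm, a 5-point rise at one dose would pass 83–89% of the time at a 5% level and about 83% at 10%. A 10-point rise would pass 36–67% and 36–56% of the time. The event rates and the level are assumptions. The 5-point conclusion does not depend on them: backgrounds of 10–15% give 91–92% at 5% and 84–85% at 10%, and pairwise testing is weaker still. For tolerability the same reasoning applies, but its size cannot be computed from the plan. Because no dose-advancement rule depends on the criterion, this is a change that should be made rather than a flaw that undermines the trial.

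**What to change.** In sections 1.1 and 3, replace *confirm* with *estimate* for safety and tolerability, and delete the absence of a significant difference as the criterion. Leave the feasibility criterion unchanged.

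In section 9.4.4, base the conclusions of the final analysis, not only the closed report, on:

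1. exact 95% confidence intervals for each active arm's rate of each of the four clinically important events and for its difference from sham, with the interval method named, stating the largest rate and largest excess not excluded;
2. the VAS location shift of each active arm against sham, with its 95% confidence interval.

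Keep the Fisher and Kruskal–Wallis tests as descriptive. Make any SAP text agree.

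The cost is wording in three sections, with no new data or subjects. The trial gives up a claim of confirmed safety from a non-significant p-value, and the reported limits will be wide: 8.2% even with no events in an arm of 43.

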lesion onto the corticospinal tract. Two studies suggested that the presence of MEPs could aid subject selection for both noninvasive⁸⁹ and invasive brain stimulation study⁹² – **subjects with MEPs are more likely to show improvements than subjects without MEPs**. Similarly, a two-center study led by Drs. [name] and [name] demonstrated that wCST-LL could effectively predict motor recovery from the acute phase to 3 months (Fig 6A) and wCST-LL of ≥ 7.0 cc in the acute phase would lead to poor motor recovery (FM-UE ≤ 25 out of 66) at 3 months¹⁶. Overall, wCST-LL provided a more graded and sensitive measure of CST injury than the clinical assessment and

correlated better with motor outcomes, especially in the severely impaired subgroup (Fig 6C and D). wCST-LL in the chronic phase is also correlated with the motor impairment measured by FM-UE scale⁹³. Furthermore, a slight variation of a CST-lesion load variable was found to be a predictor of improvement in an experimental trial in chronic stroke patients²⁰. It has not been formally investigated whether MEPs or wCST-LL or a combination of both can be used as both a predictive and prognostic biomarker in the same study.

A8. Choice of outcome measures for tDCS stroke motor recovery.

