8.1.2 EXPLORATORY AIMS MEASURES

8.1.2.1 IMAGING MEASURES

We will determine **two imaging measures**: weighted corticospinal tract lesion load (**wCST-LL**) that be derived from the pre-intervention MRI and the **fractional anisotropy (FA) measure** that will be derived from the pre- and post-intervention MRI. These imaging measures support the exploratory aims/objectives outlined in section 3 above.

wCST-LL: Three MRI sequences (T1-weighted, T2-weighted, and FLAIR imaging) will be used to define and quantify the stroke lesion. A 3D map of this lesion will be overlaid onto a canonical corticospinal tract which was derived from a group of elderly healthy control subjects and exists in our lab as a representative map of the CST; (see [name] et al., 2015 for details). The overlap area between the lesion and the canonical CST will constitute our measure of wCST-LL. The weighting of the lesion load is related to the probabilistic nature of the tract and its geometric changes while it traverses from the cortex through the internal capsule into the brainstem. The **wCST-LL** is a continuous measure expressed in cubic centimeter (cc) with 2 decimals.

Corticospinal Tract - fractional anisotropy values (CST-FA): FA values are derived from an MRI sequence called diffusion tensor imaging (DTI). FA values will be determined in maps of the CST. Canonical maps of the CST (stretching from the posterior limb of the internal capsules to the lower brainstem) exist in our laboratory and have been previously described (see Zheng and [name], 2015 for details). FA is a measure of tract integrity or how well fibers are aligned in one direction in a tract. Values are between 0-1. Fractional anisotropy values tell us something about the direction of water flow. If the value is closer to 1, water flows along major fiber tracts in one particular directions, which means that the fibers are healthy and well aligned. Typically, on the side of the stroke, we might see a decrease in FA or water not only flowing in one direction but multiple directions, reflecting a degeneration of a fibers in a tract as an effect of the stroke. FA values derived from a template of the CST on the lesional and contralesional hemisphere will be determined in the pre-intervention MRI and post-intervention MRI and changes in these FA values will be correlated with behavioral changes within the three treatment groups as specified in the SAP.

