9.4.2 ANALYSIS OF THE PRIMARY EFFICACY ENDPOINT(S)

The change in FM-UE Scale in each treatment arm will be modeled using generalized linear mixed effects repeated measures model, where the dependent variable is the change from baseline in

FM-UE to post-intervention visit; the model is adjusted for intervention arm, baseline FM-UE, time from stroke, visit and site; and the primary outcome is the fitted estimate at day 15. Model assumptions, including normality, will be assessed and appropriate transformations will be used in keeping with best practices and conventional approaches in the literature. If the primary null hypothesis is rejected, all pairwise secondary hypotheses will be tested using a Dunnett type multiple comparisons correction^{118, 119}.

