9.4.6 SUB-GROUP ANALYSES

In pre-specified subgroup analyses, the primary analysis (§9.4.2) will be repeated but include an interaction effect between sex/gender or race/ethnicity and intervention arm. Differential effects of tDCS by sex/gender or race/ethnicity are not anticipated, and therefore the trial is not powered specifically for these subgroup analyses, but these subgroup analyses will allow any unexpected large variations to be identified and regardless of outcome will assist with planning a Phase III trial which will account for differences if identified here.

Additional analyses are specified in the statistical analysis plan (SAP).

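### For the Phase III patient-selection aim, the protocol text names only correlation of wCST-LL and MEPs with FM-UE change and no biomarker-by-arm contrast, so it cannot separate prognosis from prediction

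*Combined protocol and SAP*

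**What the plan says.** The synopsis states the exploratory objective as finding out whether wCST-LL, MEPs or a combination "are correlated with changes in FM-UE scale, and evaluate the utility of these measures as biomarkers for patient selection criteria" in Phase III. Section 3 repeats it: correlation with FM-UE change, and then to "evaluate the utility of these measures as biomarkers for subject selection criteria in the future confirmatory Phase III study". Neither place gives a method for that second step.

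Section 2.2 (A.7) describes as not yet formally investigated whether these measures "can be used as both a predictive and prognostic biomarker in the same study".

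In the analysis sections:
- Section 9.4.2 gives the primary model: "the model is adjusted for intervention arm, baseline FM-UE, time from stroke, visit and site". It has no biomarker term.
- Section 9.4.6 repeats that model but will "include an interaction effect between sex/gender or race/ethnicity and intervention arm". No other arm interaction is named.
- Section 9.4 states: "Details of the statistical analyses are provided in the Statistical Analysis Plan". Section 9.4.6 also refers further analyses to the SAP. No separate SAP text was available for this review.

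Section 8.1.2.1 mentions analysis by arm, but for a different measure: "changes in these FA values will be correlated with behavioral changes within the three treatment groups as specified in the SAP". That concerns pre-to-post change in fractional anisotropy, which serves the other exploratory aim, not the baseline markers considered for selection.

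**The concern.** To choose patients for a tDCS trial, one needs to know whether the difference between tDCS and sham varies with the marker. Correlating the marker with FM-UE change asks something else: whether patients with a better-preserved tract improve more, whatever they receive.

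Here the two are easily confused. All three arms receive mCIMT, which Section 9.2 assumes yields 4.5 points alone. Section 2.2 (A.5) expects spontaneous recovery in subacute patients. The documents already regard the markers as prognostic without tDCS: Section 2.2 (A.7) reports that wCST-LL predicts recovery to 3 months, with R² = 0.47 in the severely impaired subgroup, and Section 4.2 says tract injury governs natural outcome as well as response to intervention. A positive correlation is therefore likely whether or not the marker bears on the tDCS effect.

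At stake is the advice that this trial can give on Phase III eligibility. A purely prognostic marker could look like a selection tool, and a marker that truly modifies the tDCS effect could be missed.

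**Working it through.** **The plan's own figures.** The documents give no figure for the biomarker aim, so the check starts from Section 9.2. With means 4.5, 9.0, 9.0, SD 7, 31 per arm and two-sided alpha 0.10, the noncentrality is 31 × 13.5 / 49 = 8.54, and the three-arm F test has 82.8% power (stated 83%). The inflation is 31 / 0.92² = 36.63, × 1.15 = 42.1, rounded up to 43 per arm (stated 43). Both reproduce.

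**Inputs.** SD 7, alpha 0.10, 43 per arm and 15% loss are from Section 9.2. About 20% without a recordable MEP, with a fallback index below 10%, is from Section 8.1.2.2. Marker strengths and the effect pattern of 4.5 versus 0 points are assumptions.

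**How often a purely prognostic marker is declared correlated.** Power ≈ Φ(atanh(r) × √(n − 3) − 1.645), with n = 129, or n = 129 × 0.85 ≈ 110 after loss.

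| Assumed r in every arm, no interaction | n = 110 | n = 129 |
|---|---|---|
| 0.20 (atanh 0.203) | Φ(2.10 − 1.645) = 67% | Φ(2.28 − 1.645) = 74% |
| 0.30 (atanh 0.310) | Φ(3.20 − 1.645) = 94% | Φ(3.47 − 1.645) = 97% |
| 0.40 (atanh 0.424) | Φ(4.38 − 1.645) = 99.7% | Φ(4.76 − 1.645) = 99.9% |

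**Simulation, 43 per arm, 4,000 runs, active arms pooled.**
- Prognostic only, r about 0.3 to 0.4: the pooled correlation is significant in 95% to 99.9% of trials. The interaction test rejects in about 10%, its nominal level.
- A true effect modifier (3 points per SD) with an opposite prognostic slope (−2 per SD): slopes are −2 in sham and +1 in each active arm, averaging (−2 + 1 + 1) / 3 = 0. The pooled correlation is significant in 10% of trials, the interaction test in 75%.

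**Precision of the interaction for MEP status, 20% absent.** Per arm, 34.4 have an MEP and 8.6 do not.
- Both doses against sham: SE = 7 × √(1/34.4 + 1/68.8 + 1/8.6 + 1/17.2) = 3.27, so the 90% CI is ±1.645 × 3.27 = ±5.4.
- One dose against sham: SE = 7 × √(2/34.4 + 2/8.6) = 3.77, or ±6.2.
- At n = 110 these scale by √(129/110) to about 3.5 (±5.8) and 4.1 (±6.7).
- Power for 4.5 versus 0 points, pooled: Φ(4.5/3.27 − 1.645) ≈ 40%. The difference detectable with 80% power is (1.645 + 0.842) × 3.27 = 8.1 points.
- With 10% absent, pooled: SE 4.36, power about 27%, detectable difference 10.8 points.

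**Continuous marker such as wCST-LL, pooled.** SE of the slope difference = 7 × √(1/43 + 1/86) = 1.31 per SD; detectable difference 2.487 × 1.31 = 3.3 points per SD.

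These are single-visit calculations without covariate adjustment.

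**The case against.** The strongest reply is that the analysis is deferred, not wrong. Sections 9.4 and 9.4.6 send details to a SAP that was not available, and Section 9 as seen contains no biomarker analysis of any kind, which fits deferral as well as omission. The objective also has two parts, and the part about utility for selection carries no method. This stands: a reader might infer that the trial has decided to settle patient selection by correlation, and the documents do not establish that.

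Three other stronger readings also fail:
- That a correlation shows only prognosis. A pooled correlation mixes prognostic and predictive components, and arm-specific correlations compared with sham would bear on prediction. The text does not say which is meant for wCST-LL and MEPs.
- That Section 2.2 commits the trial to separating the two uses. It records a gap in the research and sets no requirement.
- That a correlated marker will become a Phase III criterion. No rule says so, and the aim is labelled exploratory.

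It is also fair that r = 0.30 has no source in the documents, and that an interaction estimate this imprecise would probably not settle selection. None of this supplies the missing contrast. The protocol text names effect modifiers for sex/gender and race/ethnicity, where it expects no difference, and none for the markers it wants to evaluate for choosing patients.

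**Conclusion.** The concern holds as a gap in the protocol text. For an aim meant to inform Phase III selection, only correlation with FM-UE change is named, and a correlation not contrasted with sham cannot separate prognosis from prediction. The 94% to 97% chance of a significant result for a marker with no bearing on tDCS benefit rests on an assumed r = 0.30 in every arm; it is 67% to 74% at r = 0.20 and above 99% at r = 0.40. The interaction is the relevant quantity but will be imprecise: for MEP status about ±5.4 points with 43 per arm, SD 7 and 20% absent. The primary analysis and sample size are unaffected. Whether the SAP already closes the gap cannot be determined from the text available.

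**What to change.** For the selection aim, state in Section 9.4 and the SAP that the Section 9.4.2 model will be refitted with baseline wCST-LL (continuous) and MEP status, separately and together, each with a main effect and biomarker-by-arm terms estimated at day 15. Let those terms vary by visit so that later visits do not blend into the day-15 estimate. If fewer than 10% lack an MEP, use the rMT asymmetry index of Section 8.1.2.2 instead.

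Report the tDCS-minus-sham difference across marker values with 90% confidence intervals, for each dose and for both pooled. Label the correlation or main effect as prognostic. State in advance that the interaction is hypothesis-generating, with the precision and power above.

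If the SAP already contains these terms, align the synopsis and Section 3 with it.

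The cost is protocol and SAP wording plus a few model runs. The baseline MRI and TMS are already in the schedule of activities, and no new patients or data are needed. The price is wide intervals, which should be reported as such.
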